3.5 Safety Analyses

3.5.1 General Considerations

Analysis population

Safety population will be used for safety analyses of AEs, clinical laboratory data, Columbia Suicide Severity Rating Scale (C-SSRS) data, ECG data and vital sign data (all the safety data except for ARIA data). Safety MRI population will be used for analyses of ARIA data.

LTE safety treatment groups

Since all the subjects are supposed to receive active treatment in LTE, the LTE safety treatment groups which are exactly the same as the LTE randomization treatment groups will be used for all the safety analyses. Subjects who were randomized to placebo group but accidentally received one or more doses of the active treatment during the placebo-controlled period will still be classified as late start for all the safety analyses that involves LTE, but their applicable safety data in the placebo-controlled period will be included in the analysis for placebo-controlled and LTE active treatment period.

CONFIDENTIAL

The information contained herein may not be used, disclosed, or published without the written consent of Biogen MA Inc.

Safety analysis period

Analysis period will be specified for each output. Safety data in the specified analysis period will be included in the analysis. Listings will include all data in the placebo-controlled and LTE period, unless otherwise specified.

Safety analysis displays

For either analysis period in this SAP (LTE period, placebo-controlled and LTE period, or placebo-controlled and LTE active treatment period), AEs, clinical laboratory data, C-SSRS data, ECG data and vital sign data (all the safety data except for ARIA data) will be summarized by LTE treatment group (late start low dose, late start high dose, early start low dose, early start high dose, and in addition late start total, early start total and BIIB037 total; analysis display A in Appendix 4.1), unless otherwise specified. ARIA tables will be presented by LTE treatment group stratified by ApoE status (3 columns under each of the 4 LTE treatment groups: ApoE ϵ 4+, ApoE ϵ 4- and total, and in addition late start total and early start total; analysis display B in Appendix 4.1), unless otherwise specified. A subset of AE tables will also be presented by LTE treatment group stratified by ApoE status in addition to by LTE treatment group. Listings will be presented by LTE treatment group stratified by ApoE status, with an indicator of the study period (pre-dosing, placebo-controlled, or LTE) for each record when the event/assessment occurred.

LTE baseline for late start subjects

Placebo-controlled baseline is defined as the last non-missing measurement collected prior to the first dose (the baseline used for placebo-controlled period analyses). LTE baseline is defined as the last non-missing measurement collected prior to the first dose of the LTE period. For analyses on the LTE period or on the placebo-controlled and LTE active treatment period, LTE baseline will be used for late start subjects who are assigned to receiving aducanumab in the LTE period. Study day and analysis visit window for analyses using LTE baseline will be derived based on the first day of study drug in LTE.

Incidence, incidence proportion and incidence rate

- Incidence and incidence proportion will be provided in incidence tables. Incidence is defined as the number of subjects who experienced an event. Incidence proportion is defined as the number of subjects who experienced an event divided by the total number of subjects in the analysis population, i.e., percentage. Each subject will be counted only once within each category.
- Incidence and incidence rate will be provided in incidence rate tables. Two different kinds of incidence rate tables will be provided as appropriate for different analyses. Definitions are provided below.

- (1) Follow-up adjusted incidence rate – defined as the number of subjects who experienced an event divided by the total of entire follow-up time among the subjects in the analysis population. The entire follow-up time for a subject is defined as the time from the first dose until the last day on study. Each subject will be counted only once within each category.
- (2) Exposure-adjusted incidence rate (EAIR) – defined as the number of subjects who experience an event divided by the total exposure adjusted follow-up time among the subjects in the analysis population. The exposure adjusted follow-up time is defined as the time from the first dose until the initial occurrence of the event for those who experienced an event, or from the first dose until the end of follow-up (the last day on study) for those who did not. Each subject will be counted only once within each category.

3.5.2 Clinical Adverse Events

Treatment-emergent AEs (TEAEs)

All AEs will be analyzed based on the principle of treatment emergence. A treatment-emergent AE was defined as an AE that started or worsened after the start of first infusion of study treatment.

To define treatment emergence for AEs with missing start or stop date or time the following additional criteria will be used:

- if both the start and stop dates for a particular AE are missing, then that AE is considered treatment emergent;
- if the start date for a particular AE is missing and the stop date/time falls after the first dose date/time, then that AE is considered treatment emergent;
- if the start date for a particular AE was the same as the first dose date, and the start time was missing, then that event is considered treatment emergent.

For AEs with a partial start date, the year/month of the event date will be compared to that of the first dosing date to determine whether the event is treatment emergent.

In addition, SAEs that occurred since a subject was screened in the study and prior to the first infusion of study treatment, which by definition are not treatment-emergent, will be analyzed separately.

Only TEAEs will be included in the AE tables, unless otherwise specified. Listings of AEs will include all events, whether treatment-emergent or not.

As specified in the protocol, subjects were expected to return to the study site for an End of Study visit 18 weeks after the last administration of study treatment. However, some subjects may elect to continue study participation on a modified schedule after discontinuing treatment, possibly in substantial excess of 18 weeks. For most general AE summaries, AEs with an onset more than 18 weeks after the last dose will be excluded (will specify in the footnote of the specific table). For incidence rate analyses excluding AEs more than 18 weeks after the last dose, the “last day on study” in follow-up time calculation will be replaced with

“18 weeks after last dose or last day on study, whichever earlier”. Summaries of deaths and AEs leading to study withdrawal, and other selected analyses will include all AEs regardless of the time since the last dose. Listings will include all AEs, unless otherwise specified.

3.5.2.1 Summary and incidence analysis

Overall summary of AE table will be done for the LTE period, as well as for the placebo-controlled and LTE active treatment period presented by LTE treatment group as well as LTE treatment group stratified by ApoE status. The following information will be summarized: the number of subjects with any AE, with any AE by maximum severity, the number of subjects with any related AE (related to study drug as assessed by investigator), the number of subjects with SAE, the number of subjects with related SAE, the number of subjects with AE leading to study drug discontinuation, the number of subjects with AE leading to study withdrawal, and the number of deaths.

The sorting order of AE incidence tables, unless otherwise specified, will be by decreasing frequency order of “BIIB037 total” column within each category in the tables presented by LTE treatment group, and by decreasing frequency order of “BIIB037 early start total” column within each category in the tables presented by LTE treatment group stratified by ApoE status. A subject is counted only once within each category in each table. For example, for the table of AEs by system organ class and preferred terms sorted by decreasing frequency presented by LTE treatment group, system organ class will be presented in decreasing frequency order of BIIB037 total column, and within each system organ class, preferred terms will be presented in decreasing frequency order of BIIB037 total column. A subject is counted only once within each system organ class and preferred term.

The following AE incidence tables will be provided for the LTE period (presented both by LTE treatment group and by LTE treatment group stratified by ApoE status, unless otherwise specified):

1. AEs by system organ class and preferred term sorted by decreasing frequency
2. AEs by system organ class and preferred term sorted by alphabetical order analysis (by LTE treatment group)
3. AEs by system organ class, high level group term and preferred term (by LTE treatment group)
4. AEs by system organ class (by LTE treatment group)
5. AEs by preferred term
6. AEs with an incidence of 5% or more in any treatment group by preferred term
7. Severe AEs by system organ class and preferred term
8. Severe AEs by preferred term (by LTE treatment group)
9. AEs by maximum severity by system organ class and preferred term (by LTE treatment group) (System organ class will be presented alphabetically. Preferred terms will be presented in decreasing frequency order. Maximum severity will be presented within each preferred term in the order of mild, moderate, severe, unknown and total.

CONFIDENTIAL

The information contained herein may not be used, disclosed, or published without the written consent of Biogen MA Inc.

A subject will be counted only once at the maximum severity within each system organ class and preferred term.)

10. AEs by maximum severity by preferred term (by LTE treatment group) (Preferred terms will be presented in decreasing frequency order. Maximum severity will be presented within each preferred term in the order of mild, moderate, severe, unknown and total. A subject will be counted only once at the maximum severity within each preferred term.)
11. Related AEs by system organ class and preferred term
12. SAEs by system organ class and preferred term
13. SAEs by preferred term
14. Related SAEs by system organ class and preferred term
15. AEs that led to discontinuation of study treatment by system organ class and preferred term
16. AEs that led to withdrawal from study by system organ class and preferred term
17. SAEs with fatal outcome by system organ class and preferred term
18. AEs that occurred within 2 hours from infusion start by system organ class and preferred term (by LTE treatment group)

The following listings will be provided for the placebo-controlled and LTE period:

1. Listing of AEs
2. Listing of SAEs
3. Listing of AEs that led to discontinuation of study treatment
4. Listing of AEs that led to withdrawal from study
5. Listing of AEs that occurred within 2 hours from infusion start
6. Listing of AEs related to PET ligands
7. Listing of SAEs with fatal outcome
8. Listing of AEs for subjects with treatment-emergent positive anti-BIIB037 antibody

3.5.2.2 Incidence and incidence rate analysis for placebo-controlled and LTE active treatment period

Due to the different length of placebo-controlled and LTE active treatment period in early start versus late start subjects, both incidence tables and follow-up adjusted incidence rate tables will be used for AE analyses in this period. The entire follow-up time is from the first dose in active treatment period (first dose in placebo-controlled period for early start subjects and first dose in LTE period for late start subjects) until the last day in the study.

	Statistical Analysis Plan Long-Term Extension Period	Final V1.0
---	---	-------------------

The following incidence and follow-up adjusted incidence rate tables will be provided for the placebo-controlled and LTE active treatment period (presented both by LTE treatment group and by LTE treatment group stratified by ApoE status, unless otherwise specified):

1. AEs by system organ class and preferred term sorted by decreasing frequency
2. AEs by system organ class, high level group term and preferred term (by LTE treatment group)
3. AEs by preferred term
4. Severe AEs by system organ class and preferred term (by LTE treatment group)
5. Severe AEs by preferred term
6. Related AEs by system organ class and preferred term
7. SAEs by system organ class and preferred term
8. SAEs by preferred term
9. Related SAEs by system organ class and preferred term

3.5.3 ARIA - AE of Special Interest

3.5.3.1 Background

Please refer to the placebo-controlled SAP for details.

3.5.3.2 Incidence and summary of ARIA

Incidence of ARIA-E, ARIA-H, ARIA-E and ARIA-H (not necessarily concurrent), concurrent ARIA-E and ARIA-H, ARIA-E or ARIA-H, isolated ARIA-H (only ARIA-H, no ARIA-E), ARIA-H microhemorrhage, ARIA-H macrohemorrhage and ARIA-H superficial siderosis in the LTE period and in the placebo-controlled and LTE active treatment period will be summarized based on both AE eCRF and MRI data. If there is any discrepancy in incidence between the two data sources, a listing of the subjects and ARIA events with discrepancy will be provided. In addition, the incidence table based on AE eCRF source will also be done by LTE treatment group (analysis display A in Appendix 4.1).

Number of subjects with each type of ARIA, maximum severity and worst symptomatic status of the type of ARIA being analyzed in the LTE period and in the placebo-controlled and LTE active treatment period will be summarized based on AE eCRF. For subjects with symptomatic ARIA, the maximum severity of symptoms will also be summarized.

Summary of concurrent ARIA-E and ARIA-H will be provided including the following information for the LTE period and for the placebo-controlled and LTE active treatment period: number of subjects with concurrent ARIA-E and ARIA-H (and further broken down to each type of ARIA-H), the severity of ARIA-E based on MRI, the symptomatic status of ARIA-E, the severity of symptoms based on AE eCRF. For subjects with recurrent ARIA-E

CONFIDENTIAL

The information contained herein may not be used, disclosed, or published without the written consent of Biogen MA Inc.

events, if there is an event concurrent with ARIA-H, it will be used for the summary, and the first concurrent event will be used if there are more than one event concurrent with ARIA-H.

An incidence table of AEs considered by the investigator to be related to ARIA by system organ class and preferred term for subjects with symptomatic ARIA in the placebo-controlled and LTE active treatment period will be provided, as well as a listing of these AEs. Similarly, an incidence table of AEs related to ARIA for subjects with symptomatic ARIA and severe symptoms will be provided, as well as a listing of these AEs.

Listings of AE records for each type of ARIA events and listings of MRI assessments for subjects with each type of ARIA events will be provided.

Montreal Cognitive Assessment (MOCA) is performed at baseline, Week 80 (the first visit in LTE) and each unscheduled ARIA monitoring visit for ARIA subjects (approximately every 4 weeks) except for mild asymptomatic microhemorrhage subjects. An incidence table of late start subjects with ARIA events only in the LTE period (no ARIA in the placebo-controlled period) whose MOCA total scores decrease 2 points or more from Week 80 will be provided. Since Week 80 MOCA was not a planned study event until protocol version 4, some subjects may not have a Week 80 MOCA score. For these subjects, their Week 80 MOCA will be imputed as their baseline MOCA plus the mean change from baseline at Week 80 from subjects who have a Week 80 MOCA and did not experience any ARIA in the placebo-controlled period within each treatment group and ApoE status. A listing of MRI assessments and MOCA total score for subjects with ARIA events in either placebo-controlled or LTE period will be provided.

3.5.3.3 Summary of recurrent ARIA-E

Follow-up adjusted incidence rate of subjects with ARIA-E, with 2 or more events of ARIA-E, with 3 or more events of ARIA-E and with more than 3 events of ARIA-E over their entire follow-up time for the placebo-controlled and LTE active treatment period will be summarized based on AE eCRF.

Number of total ARIA-E events in the placebo-controlled and LTE active period and the MRI severity of each event will be summarized based on AE eCRF. Number of symptomatic ARIA-E events in the placebo-controlled and LTE active period, and the severity of the symptoms of each symptomatic event will be summarized based on AE eCRF.

Summary of first ARIA-E events table based on AE eCRF will summarize the number of subjects with a first event of ARIA-E, the MRI severity of the events, the symptomatic status of the events, the severity of the symptoms for symptomatic events, whether SAE or not, number of resolved and unresolved events, duration of the resolved events, time from first active infusion in study to onset, number of doses received since the start of the period to onset, dose level of the last infusion received prior to onset, dosing status (continue as planned, dose interrupted, dose reduced, or dose discontinued) after the events, and the number of subjects with recurrent ARIA-E events. This table will be done on the placebo-controlled and LTE active treatment period. The same summary of first ARIA-E events table will also be done on the subset of subjects who had recurrent ARIA-E events.

Summary of recurrent ARIA-E events table based on AE eCRF will summarize the following information for both the second and third event of ARIA-E events: the number of subjects

CONFIDENTIAL

The information contained herein may not be used, disclosed, or published without the written consent of Biogen MA Inc.

	Statistical Analysis Plan Long-Term Extension Period	Final V1.0
---	---	-------------------

with the previous event of ARIA-E, the number of subjects with at least one dose and one MRI after the previous ARIA-E resolution, the number of subjects with this event of ARIA-E, the MRI severity of the events, the symptomatic status of the events, the severity of the symptoms for symptomatic events, whether SAE or not, number of resolved and unresolved events, duration of the resolved events, time from first infusion in study (active or placebo) to onset, time from previous resolution to onset, number of doses received since the start of the period to onset, dose level of the last infusion received prior to onset, dosing status (continue as planned, dose interrupted, dose reduced, or dose discontinued) after the events. The number of subjects with more than 3 events of ARIA-E, and the number of subjects who discontinued study treatment after recurrent ARIA-E onset will also be summarized. This table will be done on the placebo-controlled and LTE active treatment period.

A listing of subjects who withdrew from the study with unresolved ARIA-E or subjects with ongoing ARIA-E at the time of data cutoff (also considered as unresolved) will be provided with the details of the event including the duration from onset to last follow-up.

For subjects with recurrent ARIA-E, a listing of study drug administration, MRI assessments, severity and symptomatic status of each event, and end-of-treatment reason (if present) will be provided.

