	Late Start High Dose – ApoE ε4 (-)	1	1	3	3	6	6	10	
Late Start Low Dose	Late Start Low Dose – ApoE ε4 (+)	1	1	3					
	Late Start Low Dose – ApoE ε4 (-)	1	1	3	3	3	3	6	

¹ ApoE ε4 status recorded in the Interactive Voice/Web Response System (IXRS).

Individual dose adjustments may be implemented in subjects who develop amyloid related imaging abnormalities (ARIA). See Protocol Section 7.2.1.

The total duration of study participation for each subject only participating in the placebo-controlled period of the study will be up to approximately 102 weeks, including a series of screening visits within 8 weeks before administration of the first dose, a 76-week placebo-controlled treatment period, and a safety follow-up (FU) period of approximately 18 weeks after the final dose. The total duration of study participation for each subject participating in the placebo-controlled period and the LTE period will vary and be up to approximately 362 weeks, including a series of Screening visits within 8 weeks before administration of the first dose, a 76-week placebo-controlled treatment period, a 4-week FU period, a 256-week aducanumab dose-blind treatment period, and a safety FU period of approximately 18 weeks after the final dose.

[figure not shown]
Investigators, study site staff (except for the designated unblinded pharmacist/technician), and study subjects will be blinded to the subjects' randomized treatment assignment for the placebo-controlled period. During the LTE period, investigators and subjects will remain blinded to the treatment assignment in the placebo-controlled period and the aducanumab dose for the LTE period.

CONFIDENTIAL

The information contained herein may not be used, disclosed, or published without the written consent of Biogen MA Inc.

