3.1.2 Analyses period

Depending on the purpose, different analyses will be conducted on the following study periods:

1. LTE period. Only data in the LTE period will be included in these analyses. For example, incidence table of adverse events in the LTE period.
2. Placebo-controlled and LTE period. All the data in the placebo-controlled and LTE periods will be included in these analyses. For example, mean plot of actual laboratory values in the placebo-controlled and LTE period.
3. Placebo-controlled and LTE active treatment period. Active treatment period is defined as the study period(s) that a subject is assigned to aducanumab. For early start subjects – subjects who are assigned to aducanumab in both placebo-controlled and LTE period, all the data (placebo-controlled and LTE periods) will be included in the analyses. For late start subjects – subjects who are assigned to aducanumab in the LTE period, only data in the LTE period will be included. For example, incidence table of adverse events in the placebo-controlled and LTE active treatment period.

Subjects to be included in a certain output is determined by both the analysis population and the analysis period. For example, the incidence table of adverse events in the LTE period will include subjects in the safety population for the LTE period, i.e., all randomized subjects who received at least one dose of study treatment in the LTE period. The incidence table of adverse events in the placebo-controlled and LTE active treatment period will include subjects in the safety population for the active treatment period, i.e., all randomized subjects who received at least one dose of study treatment in the active treatment period. In this SAP we do not separately define the analysis population in each analysis period.

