3.5.3.4 Exposure adjusted analysis

Exposure adjusted incidence rate of ARIA-E events will be summarized based on safety MRI data for the placebo-controlled and LTE active treatment period. The exposure adjusted follow-up time is from the first active dose until the initial occurrence of ARIA-E for those who experienced ARIA-E, and until the end of follow-up for those who did not. Since ARIA is an MRI finding, the day of the last MRI assessment in the placebo-controlled and LTE active treatment period will be used as the end of follow-up for those who didn't experience the event.

Study drug administration information prior to first ARIA-E onset will be summarized for ARIA-E subjects for the placebo-controlled and LTE active treatment period, including number of total infusions, number of infusions at each dose level (placebo, 1 mg/kg, 3 mg/kg, 6 mg/kg and 10 mg/kg), dose level of the last infusion, maximum dose level received, and cumulative dose as a continuous variable.

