3.5.3.5 Time to event analysis

Kaplan-Meier plot of time to first ARIA-E event will be produced based on safety MRI data for the placebo-controlled and LTE active treatment period. Only ARIA-E events that occurred during this period will be included. Time to event is calculated as date of the MRI assessment that initially detects the ARIA-E event - date of the first active infusion +1. Censor time for subjects without ARIA-E is calculated as date of the last MRI assessment in the study - date of the first active infusion +1. Estimated proportion with ARIA-E and number of subjects at risk at selected timepoints will also be presented. The plot will be presented by LTE treatment group stratified by ApoE status.

CONFIDENTIAL

The information contained herein may not be used, disclosed, or published without the written consent of Biogen MA Inc.

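### LTE SAP 3.5.3.3 times recurrent ARIA-E from the first infusion of any kind but first ARIA-E from the first active infusion, adding about 80 weeks for late-start subjects; some late-start row labels in Tables 5 and 7 also do not match their windows

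*SAP*

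**What the plan says.** LTE SAP 3.5.3.3 plans one table for first ARIA-E events and one for second and third events. The first-event table reports "time from first active infusion in study to onset". The recurrent-event table reports "time from first infusion in study (active or placebo) to onset, time from previous resolution to onset". The same sentence closes the description of each: "This table will be done on the placebo-controlled and LTE active treatment period". Under LTE SAP 3.1.2, late-start subjects enter that period with their LTE data alone.

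The neighbouring sections use the active-treatment origin. In 3.5.3.4, "The exposure adjusted follow-up time is from the first active dose until the initial occurrence of ARIA-E"; in 3.5.3.5, time to first ARIA-E subtracts the "date of the first active infusion +1". Section 3.5.2.2 likewise starts adverse-event follow-up at the first dose of the active treatment period.

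Table 5 (laboratory) and Table 7 (antibodies) state in their footnotes that windows are counted from the first aducanumab dose. Each has one column of windows for early-start subjects and one for late-start subjects, under a single shared set of week labels. When a window holds several records, the one nearest the target visit day is used, but neither table lists target days.

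**The concern.** A late-start subject's first infusion in the study is placebo. Timing a recurrence from it brings the whole placebo-controlled period into a table meant to describe active treatment. For early-start subjects the two origins coincide, so the distortion falls on one side of the early-start versus late-start display. It also separates the two ARIA-E tables: a late-start subject's first event sits on the active clock and the second on the study clock. ARIA is the trial's adverse event of special interest, and readers will look at how late recurrences occur.

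In Tables 5 and 7 the question is whether the printed week describes the samples in the row. Where it does not, early-start and late-start samples taken after different lengths of exposure appear under one label. A programmer who takes the missing target day from the label may also select the wrong record.

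**Working it through.** **Recurrent ARIA-E**

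Inputs: a 76-week placebo-controlled treatment period plus 4 weeks of follow-up before the LTE (LTE SAP 2.1), and Week 80 as the first LTE visit (3.5.3.2).

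- Shift for late-start subjects: 76 + 4 = 80 weeks.
- Example: first ARIA-E at LTE week 20, second at LTE week 40. The first-event table reports 20 weeks. The recurrent table reports 80 + 40 = 120 weeks.
- Read together, the two tables suggest a gap of 120 − 20 = 100 weeks. The true gap is 40 − 20 = 20 weeks.
- Early-start subjects: no shift.

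The recurrent table is also inconsistent within itself. It counts doses from the start of the period but time from the first infusion in the study. The timing phrase is the same as in section 4.5.3.3 of the placebo-controlled SAP, where it does no harm, so it looks carried over.

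**Window limits in Tables 5 and 7**

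Rule: day of week w = 7w + 1, and each window starts at the midpoint of adjacent visit days.

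Check on the early-start limits:
- Laboratory, weeks 104, 128, 152, 176, 232, 284, 336: midpoints 813, 981, 1149, 1429, 1807, 2171, all as printed.
- Antibody, weeks 80, 104, 128, 152, 182, 338: midpoints 645, 813, 981, 1170, 1821, all as printed. The antibody Week 78 window starts at 471 against a midpoint of 470, a one-day difference.

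For late-start subjects, move the LTE visits to the first LTE dose (study week minus 80).

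Antibody: 104, 128, 152, 182, 338 become weeks 24, 48, 72, 102, 258 (days 169, 337, 505, 715, 1807).
- (169 + 337)/2 = 253
- (337 + 505)/2 = 421
- (505 + 715)/2 = 610
- (715 + 1807)/2 = 1261

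All four equal the printed limits. The printed labels would instead give 281, 470, 638 and 1002.

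Laboratory: 104, 128, 152, 176, 232, 284, 336 become weeks 24, 48, 72, 96, 152, 204, 256 (days 169, 337, 505, 673, 1065, 1429, 1793). Midpoints: 253, 421, 589, 869, 1247, 1611. The first five match; the sixth is printed as 1709. The printed labels would give 253, 421, 617, 897, 1345 and 1807.

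| Table | Late-start labels | Weeks since first aducanumab | Label minus week |
|---|---|---|---|
| 7, antibody | 24, 56, 78, 104, 182 | 24, 48, 72, 102, 258 | 0, +8, +6, +2, −76 |
| 5, laboratory | 24, 48, 72, 104, 152, 232, 284 | 24, 48, 72, 96, 152, 204, 256 | 0, 0, 0, +8, 0, +28, +28 |

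Four of five antibody labels and three of seven laboratory labels are off. Week 284 after first aducanumab cannot occur in a late-start subject: the plan gives "a 256-week aducanumab dose-blind treatment period" and about 18 weeks of follow-up, and 256 + 18 = 274.

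Effect on record selection: the late-start antibody row labelled Week 182 runs from day 1261 onward. The label implies a target day of 7 × 182 + 1 = 1275. An unscheduled sample on day 1300 lies 25 days from 1275, while the scheduled day-1807 sample lies 532 days away, so the unscheduled one would be used. With day 1807 as target, the scheduled sample would be used.

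**The case against.** A reader might infer that the LTE SAP puts late-start subjects on a wrong time axis throughout. The document does not support that. Tables 5 and 7 count days from the first aducanumab dose, and section 3.5.1 sets the same clock for analyses using the LTE baseline. The wrong origin is confined to the recurrent ARIA-E table; elsewhere only labels and one limit are in question.

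The labels also have an innocent reading. Both groups share one set of rows, and each late-start antibody visit sits in its nearest available row: 48 in 56, 72 in 78, 102 in 104, and 258 in 182 (76 weeks away, against 80 to Week 338). This may explain the antibody labels, but the plan does not say so, and a row 76 weeks off is still misleading. It does not explain laboratory Week 284, since week 256 is nearer to 232 (24 weeks) than to 284 (28 weeks).

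It is also tempting to declare day 1611 the correct laboratory limit. The late-start schedule is inferred here, because the LTE SAP refers to the protocol for it, and this limit is the one that does not fit. The origin of 1709 is unclear: it is both (1429 + 1989)/2 and (1625 + 1793)/2. On the inferred schedule, days 1429 and 1793 fall in the same windows under either limit; only off-schedule samples on days 1611 to 1708 would move.

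Finally, the affected ARIA-E item is one descriptive row that openly says active or placebo. Time from previous resolution and number of doses since the start of the period do not depend on that origin, and the exposure-adjusted rate and Kaplan-Meier plot use the active origin. This limits the damage but does not remove the contradiction within 3.5.3.3.

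**Conclusion.** The contradiction on recurrent ARIA-E holds on the text alone and should be corrected. Its size is about 80 weeks on every late-start time from first infusion to second or third event, and nothing for early-start subjects. The figure assumes that the first active infusion is the first LTE dose, at about Week 80.

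The table point is secondary. The mismatched labels are antibody 56, 78, 104 and 182, and laboratory 104, 232 and 284. It rests on reconstructing late-start visits as study week minus 80, which reproduces all four antibody limits and five of six laboratory limits. The 1708/1709 limit is an open discrepancy, not a proven error.

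Every affected output is a descriptive safety summary. No efficacy test and no ARIA incidence changes.

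**What to change.** 1. In the recurrent-event paragraph of LTE SAP 3.5.3.3, count time to onset from the first active infusion, as the first-event table, 3.5.3.4 and 3.5.3.5 already do.
2. In Tables 5 and 7, relabel the late-start rows by weeks since first aducanumab, or add a target-day column for each group. If the shared rows were intended as nearest matches, say so in a footnote and still give the target days.
3. Reconcile the late-start laboratory limit 1708/1709 with the visit schedule in the protocol. The midpoint rule behind the other limits would give 1610/1611.
4. Check the late-start vital-sign row in Table 6 labelled Week 260 at the same time. Its start, day 1800, is the midpoint of weeks 256 and 258: (1793 + 1807)/2.

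The cost is one phrase, some row labels or target days, and a check of one limit. No new data are needed.
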